1.0 INTRODUCTION

While allogeneic hematopoietic cell transplantation (HCT) is currently the only curative treatment modality for myelodysplastic syndrome (MDS), relapse remains a major cause of failure. Pre-HCT cytoreductive therapy has been utilized with regularity to reduce post-HCT relapse. – at our institution among 141 MDS patients transplanted over the past three years 130 (92%) received prior chemotherapy (unpublished data) – however, the optimum modality, and the impact on post-HCT outcome remain to be determined. Since MDS is primarily a disease of older age, often complicated by comorbidities, a major concern with induction chemotherapy (IC) as used for acute myeloid leukemia is treatment-related toxicity and mortality. Treatment-related toxicities are likely to affect patients' candidacy for and capacity to tolerate the subsequent HCT. Recently, many patients have received pre-HCT cytoreduction with hypomethylating agents (azacitidine and decitabine), rendered attractive by ease of administration and a low toxicity profile. Although there is a growing body of retrospective literature, no randomized prospective trials comparing IC with hypomethylation have been performed.

We are conducting a prospective trial randomizing patients with intermediate and high-risk MDS who are HCT candidates to receive pre-HCT therapy with IC versus hypomethylation. The primary aim is to prospectively assess the impact of IC versus hypomethylation as initial therapy on survival in the study population. We will also assess transplant frequency, relapse, and quality of life. Results from this study will provide controlled, prospective data on the impact of pre-HCT IC versus hypomethylating therapy on transplantability and transplant outcome, thereby guiding clinical practice.

2.0 BACKGROUND

2.1 Study Disease

MDS represents a group of clonal myeloid stem cell disorders with a heterogeneous spectrum of presentation, ranging from an indolent course over several years to rapid progression to acute myeloid leukemia (AML). MDS typically occurs without a preceding insult (*de novo* MDS) but can also occur after chemotherapy or radiotherapy resulting in secondary MDS. The natural history of patients with MDS is varied with a median survival ranging from 5.7 years for patients with low-risk IPSS (International Prognostic Scoring System) scores, to 0.4 years for those with high-risk scores [1]. Although some conventional therapies have been shown to prolong survival, the only treatment modality for MDS with demonstrated curative potential is allogeneic hematopoietic cell transplantation.

With a median age at the time diagnosis of 65 years, the care of patients with MDS is often complicated by medical comorbidities, and treatment considerations revolve around a balance of the benefit and tolerability of a given modality. Historically, transplantation had been reserved for the young and fit with related donors as the intensive conditioning led to high rates of transplant-related mortality. As a result of improved conditioning regimens, prevention of liver toxicity with ursodiol, and improved microbial surveillance, prevention, and treatment with reduced complications from cytomegalovirus and fungal infections HCT outcomes have improved over time [2]. Furthermore, the development of reduced intensity conditioning (RIC) regimens has extended transplantation to patients with increasing age and comorbidities. Currently, over 60% of patients undergoing HCT for MDS are conditioned with a reduced intensity regimen.

Despite the curative potential of HCT, relapse remains the primary cause of failure after transplantation [3-5]. The risk of relapse not only correlates with intrinsic disease properties such as cytogenetics, but also with the total disease burden. Although there is less non-transplant-related mortality with RIC regimens, there is an increase in relapse as compared to conventional high-dose regimens [4,5]. This result is thought to be due to the fact that little disease reduction occurs with reduced conditioning, placing more responsibility on the graft-versus-leukemia effect to clear the disease. This conclusion is supported by the fact that patients with a higher disease burden prior to

HCT, regardless of conditioning regimen, experience increased rates of relapse as compared to those in remission [4,5].

2.2 Clinical Data to Date

The strategy of using chemotherapy prior to transplantation in an attempt to reduce disease burden, therefore reducing the risk of relapse after HCT, has become commonplace. Nevertheless, in the absence of randomized prospective trials the role of pre-HCT cytoreduction remains undefined. Prior to 2004, the mainstay of cytoreduction was intensive chemotherapy regimens developed as induction therapy for AML though retrospective studies of these regimens before HCT have not pointed to a clear benefit [6-8]. Furthermore, intensive pre-HCT therapy may lead to a worsening in performance status impacting patients' candidacy for and capacity to tolerate the subsequent HCT [9].

More recently, hypomethylating agents (azacitidine and decitabine) have increasingly been used for pre-HCT cytoreduction rendered attractive by their ease of administration and a low toxicity profile in an attempt to better balance cytoreduction and treatment-related toxicity. In the absence of prospective data, several groups have published the results of retrospective analyses noting the feasibility of this approach [10-12]. We recently reported our experience in 68 patients who underwent HCT for MDS who received either induction chemotherapy or azacitidine prior to HCT [13]. The 1-year overall survival after transplant was 57% in the azacitidine group, and 36% in the group given induction chemotherapy. Although the risk of post-HCT relapse and non-relapse mortality was lower in the azacitidine group, none of the differences including overall survival were statistically significant suggesting that at a minimum azacitidine did not confer worse outcomes when compared to induction chemotherapy.

2.3 Study Agent

This study does not prescribe a specific study agent, but rather a treatment strategy with a particular class of agents as the backbone of each treatment strategy. Therefore, a description of the study agent, its make-up, chemical properties and any relevant physical properties is not applicable. If patients are subsequently enrolled on an additional study for treatment after randomization on the present study, please refer to the protocols of the other studies for information regarding the specific agents of those studies. If patients are not enrolled on other studies, the agents administered as part of the treatment plan will be at the discretion of the attending physician.

2.4 Risks/Benefits

There is a potential risk of increased toxicity and death with intensive chemotherapy over that of hypomethylating agent-based therapy. However, this risk will be mitigated by selecting patients who are deemed to have an adequate level of fitness to receive intensive chemotherapy. In the prospective AZA 001 study [14], patients selected for and who received intensive chemotherapy had comparable rates of early treatment-related mortality and grade 3/4 toxicity compared to those who received azacitidine. Based on the available data, it is reasonable to conclude that cytoreduction prior to transplant can improve the rates of post-HCT relapse, thereby improving the overall outcome for patients with MDS. The knowledge gained from the present study will help identify the optimal pre-HCT cytoreductive strategy.

3.0 STUDY OBJECTIVES

3.1 Primary Objectives

The primary objective is to determine the effect of IC (intensive AML-like therapy), versus less intensive hypomethylating agents (HMA) as initial therapy, on failure-free survival. We will test the hypothesis that HMA will lead to failure-free survival that is at least as good as that with IC.

3.2 Secondary Objectives

Determine if IC (intensive AML-like therapy) in comparison to HMA as initial therapy, will affect transplantation frequency, and quality of life. Conduct exploratory analysis of post-HCT outcomes (overall survival, and relapse).

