4.2.2 Secondary Endpoints

1. Frequency at which the patients undergo transplantation
2. Impact on quality of life
3. Post-transplant outcomes:
 - a. Overall Survival
 - b. Relapse

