7.4 Duration of Therapy (Treatment Phase)

Duration of study therapy will depend on response and donor availability. Please see Appendix C for definitions of response criteria. For patients enrolled on concurrent treatment protocols, assessment of response as dictated by the treatment protocol will take precedence over the following treatment response evaluation and treatment duration guidelines.

The specific treatment agents and schedule will vary per patient within both study arms (please see section 7.1 for details). These agents and schedules will be determined by treatment protocols, institutional standards, or physician preference. Follow-up prior to each cycle of therapy will also be determined by treatment protocols, institutional standards, or physician preference.

Patients randomized to either arm must receive at least one cycle of therapy. If at any point after the administration of the first cycle of therapy a donor is available, the patient may proceed to HCT.

Patients may receive additional cycles of treatment to maintain response while waiting for donor availability. However, continued therapy should not be used to delay available HCT. If patients demonstrate disease progression at any point after the first cycle, they should discontinue the study treatment.

For patients who are receiving decitibine-based therapy under Arm A, it is recommended that a bone marrow biopsy or aspirate be obtained after 2 to 4 cycles to assess response. For patients who are receiving azacitidine-based therapy under Arm A, it is recommended that a bone marrow biopsy or

aspirate be obtained after 4 to 6 cycles to assess response. If at that point stable disease or better is achieved and a donor is available, the patient may proceed to HCT. If the desired degree of response or cytoreduction has not been met by 4 cycles of decitabine-based therapy, or 6 cycles of azacitidine-based therapy patients should be offered alternative treatments.

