For patients randomized to Arm B, response to therapy will be determined by bone marrow biopsy or aspirate 28 (+/- 3) days after the start of therapy or at the time of count recovery. If a desired response is achieved, the patient may proceed to HCT. If a less-than desired response is achieved with the first cycle of intensive chemotherapy, it is recommended that the patient receive an additional cycle of intensive therapy (re-induction). If after re-induction a partial remission or better is achieved, the patient may proceed to HCT. However, if the patient has stable disease or disease progression, the patient should be offered alternative treatment or proceed directly to transplant if possible. .

If at any point a patient no longer desires to undergo HCT, or is no longer considered an HCT candidate, the patient will be withdrawn from the study. However, the patient may go on to receive the assigned treatment off study protocol.

The number and timing of clinic visits or scheduled inpatient admissions will be determined by either the primary treatment protocol or at the discretion of the attending physician.

Treatment phase evaluations are outlined in the study calendar (Appendix D). After initial treatment and before transplant, complete the EORTC-QLQ-C30 and EORTC-QLQ-HDC29 questionnaires.

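### Overall survival is planned only after transplant: add a descriptive estimate in all randomized patients, and label arm contrasts after transplant as non-randomized

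*Combined protocol and SAP*

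**What the plan says.** **OS and relapse.** Section 3.2 reads "Conduct exploratory analysis of post-HCT outcomes (overall survival, and relapse". Section 4.2.2 places the same two outcomes, as items 3a and 3b, under "Post-transplant outcomes". They are thus exploratory in one section and secondary endpoints in the other.

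**Aim.** The Introduction says "The primary aim is to prospectively assess the impact of IC versus hypomethylation as initial therapy on survival in the study population". It also expects results on the effect of induction chemotherapy (IC) versus "hypomethylating therapy on transplantability and transplant outcome, thereby guiding clinical practice".

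**Primary endpoint.** Section 4.2.1 uses 18-month failure-free survival (FFS), with death and relapse both counted as failures. Section 13.0 analyses it by intention to treat, and section 7.7 also refers to intention to treat in general terms. Section 13.0 mentions OS only to say that the trial is too small to show a significant difference.

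**Data.** Section 8.0 requires deaths to be reported over each patient's 18 months, and Appendix D has a survival check 18 months after Day 1. Section 7.4 withdraws patients who are no longer transplant candidates. Under section 7.7, survival data after withdrawal from treatment need permission.

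**Quality of life.** Under section 11.3 the QLQ-C30 is collected at screening, after initial therapy and before transplant, and about 100 days after transplant. Section 13.0 plans absolute scores plus the standardized response mean (SRM), both for change over time and for group differences. It gives no formula for the group comparison and names no covariate.

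**The concern.** Transplant happens after randomization. The protocol studies its frequency as an outcome and gives a reason why the arms might differ: "intensive pre-HCT therapy may lead to a worsening in performance status", which in turn may affect candidacy. Patients transplanted in one arm may therefore differ in prognosis from those transplanted in the other. A difference in post-transplant OS, relapse or Day-100 quality of life could reflect who was transplanted and not the assigned strategy. The exploratory label does not tell a reader this.

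The OS estimate that keeps the randomized comparison is not planned, although it is the one closest to the aim in the Introduction. FFS covers every death but does not separate death from relapse, so it cannot stand in for OS.

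A separate, smaller issue concerns the SRM. If arm-specific SRMs are compared, two arms with the same mean change can appear to differ because the spread of change differs.

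**Working it through.** **1. The plan's own figures.** With 30 per arm, the exact probability that observed FFS with hypomethylating agents (HMA) is at least that with IC, for two independent binomials, is 0.959, 0.911 and 0.257 for true rates of 50/30, 45/30 and 50/60%. Section 13.0 gives 0.96, 0.91 and 0.26. These reproduce; the point is not an arithmetic error.

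**2. Selection (illustration, all inputs assumed).** Take two equal prognostic groups with the same post-transplant survival in both arms, so treatment has no effect after transplant. For the spread use 57% and 36%, borrowed from section 2.2 ("The 1-year overall survival after transplant was 57% in the azacitidine group, and 36% in the group given induction chemotherapy"). Those are results by treatment and serve here only as a plausible range. With transplant rates g (better group) and p (poorer group):

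- Post-transplant OS = (0.57g + 0.36p)/(g + p)
- Number transplanted per arm = 30(g + p)/2

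Losses in the poorer group, g = 0.8 in both arms:

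| p | OS | n |
|---|---|---|
| 0.8 | 46.5% | 24 |
| 0.6 | 48.0% | 21 |
| 0.4 | 50.0% | 18 |
| 0.2 | 52.8% | 15 |

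Difference (arm transplanting fewer minus the other), with half-width 1.96 × √(p₁q₁/n₁ + p₂q₂/n₂), where p₁ and p₂ are the two OS values and q = 1 − p:

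| p in the two arms | Difference | Half-width | Ratio |
|---|---|---|---|
| 0.6 vs 0.4 | +2.0 points | 31.5 | 6% |
| 0.8 vs 0.4 | +3.5 | 30.5 | 11% |
| 0.6 vs 0.2 | +4.8 | 33.1 | 15% |
| 0.8 vs 0.2 | +6.3 | 32.2 | 20% |

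If the losses fall in the better group (p = 0.8, g varied), OS is 46.5, 45.0, 43.0 and 40.2%, and the differences are −2.0, −3.5, −4.8 and −6.3 points. If both groups lose equally (0.8/0.8 vs 0.4/0.4), the difference is 0.

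**3. Precision of OS in all randomized patients.** The half-width for an 18-month difference, 1.96 × √(2pq/30), is 25.3 points at 50% OS, 24.8 at 60% and 23.2 at 70%. On the same footing at 50% OS, restricting to transplanted patients gives 28.3 points with 24 per arm and 35.8 with 15 per arm.

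For the hazard ratio, the 95% interval is a factor of exp(1.96 × 2/√d) either way, where d is the number of deaths. The rates in section 13.0 imply 15 + 21 = 36, 16.5 + 21 = 37.5 and 15 + 12 = 27 failures. If all were deaths, the factors are 1.92, 1.90 and 2.13. With 20 deaths (assumed) it is 2.40.

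**4. SRM.** SRM = mean change / SD of change. With an assumed mean change of −10 in both arms:

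- SD 20 in both arms: −0.50 vs −0.50
- SD 20 vs 25: −0.50 vs −0.40
- SD 20 vs 30: −0.50 vs −0.33

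If the difference in mean change is instead divided by a pooled SD, the result is 0 in every case. Section 13.0 does not say which is meant.

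**The case against.** **Deaths before transplant are not lost.** This stands. They count in FFS under intention to treat, and transplant frequency is reported too. A reader might infer that the trial ignores these deaths, or that intention to treat is confined to the primary outcome. Neither is supported, since section 7.7 uses the term without that limit. But a general reference to intention to treat does not create an OS analysis.

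**OS is underpowered.** Section 13.0 says so, and that is a sound reason not to test it. It is no reason to leave OS unestimated while planning a post-transplant version in fewer patients.

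**Arm contrasts after transplant are partly inferred.** Section 3.2 words the comparison of strategies for transplant frequency and quality of life, and section 13.0 specifies no post-transplant test. This stands, so the point concerns any such contrast that is made. The Introduction's wish to guide practice on transplant outcome makes one likely.

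**The selection effect is modest and assumed.** This stands. Its upper end needs one group's transplant rate to be 80% in one arm and 20% in the other, which no section supports.

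**The SRM is not the only quality-of-life report.** This stands. Absolute scores are planned and would partly expose a contrast driven by spread. A reader might also infer that baseline is ignored, but an SRM of QLQ-C30 change from screening already subtracts it. What is missing is a defined between-arm measure and a stated covariate.

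**Dates may already be held.** Appendix H has no column headed for randomization or death date. A reader might infer that these dates are unavailable. But randomization is done centrally (section 6.0), a death log is kept (section 8.0), and Appendix H has follow-up status and off-study fields. They need only be confirmed.

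**Conclusion.** The point holds as a gap in the planned analysis and should be closed. OS and relapse are planned only after transplant, any arm contrast there is non-randomized, and no OS estimate in all randomized patients is written. The primary FFS analysis is not affected.

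The selection effect is illustrative: 0 to about 6 points in either direction under assumed transplant rates, at most about 20% of the half-width. A reader might infer that post-transplant results will be biased towards a particular arm. The documents do not support that, because neither the transplant rates nor the prognosis of those lost is known. The firmer loss is that a randomized OS estimate goes unreported.

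The SRM issue depends on which reading is used and is softened by the absolute scores.

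The quality-of-life comparison before transplant has limits of its own. Azacitidine patients are recommended to have a marrow "aspirate be obtained after 4 to 6 cycles to assess response", whereas Arm B is assessed "28 (+/- 3) days after the start of therapy or at the time of count recovery". One might infer a fixed gap between arms. Section 7.4 does not support one: it has a shorter decitabine schedule, allows re-induction, and permits transplant after the first cycle if a donor is available.

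**What to change.** 1. **Add descriptive OS from randomization in all randomized patients.** Report Kaplan-Meier curves by arm and a hazard ratio with 95% CI, stated not to be a powered test. Section 7.5 counts follow-up from treatment Day 1, so define 18 months from randomization for patients who never start treatment. Include withdrawn patients where permission allows, and report missing data by arm.
2. **Label post-transplant OS, relapse and Day-100 quality of life by arm as descriptive and non-randomized**, beside the number transplanted per arm. Use time-to-event methods for OS and relapse, censored at the end of follow-up, because time observed after transplant depends on when transplant occurs. Treat death without relapse as a competing risk for relapse. Give these outcomes the same status in sections 3.2 and 4.2.2.
3. **For the QLQ-C30 after treatment and before transplant**, report the between-arm mean difference with 95% CI, adjusted for the screening score (ANCOVA). Keep the SRM for within-arm change. Report the number with both questionnaires and the time from Day 1, by arm. State that death, withdrawal and differing assessment times limit this comparison.

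**Cost.** Wording in the statistical section, a little more analysis, a defined window for never-treated patients, and confirmation that dates of randomization and of death or last contact are in the dataset. No new clinic visits are needed. The OS estimate will be imprecise, and some early censoring after withdrawal is likely.

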4.0 STUDY DESIGN

4.1 Description of Study

This study is a multi-center, open-label randomized study of intensive chemotherapy versus hypomethylating agent-based therapy as the initial pre-transplant cytoreductive therapy in patients with myelodysplastic syndrome.

Patients will be randomized to receive treatment with either hypomethylating agent therapy or intensive chemotherapy; they will not receive both.

4.2 Endpoints

4.2.1 Primary Endpoint

18-month failure-free survival (failure defined as death or relapse)

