5.0 SUBJECT SELECTION

5.1 Inclusion Criteria

5.1.1 Disease Criteria

1. Diagnosis of *de novo* or secondary MDS, including chronic myelomonocytic leukemia, as defined by the 2008 World Health Organization Classification System.
2. Patients must have measurable disease requiring cytoreduction, defined as a bone marrow myeloblast count $\geq 5\%$ and $< 20\%$ on morphologic examination or by flow cytometry in cases in which adequate morphologic examination is not possible.

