11.0 ASSESSMENT OF EFFICACY

11.1 Efficacy Parameters

The primary outcome is 18-month failure-free survival (failure defined as death or relapse).

Relapse will be as defined by the International Working Group (IWG) response criteria in myelodysplasia (Cheson, et. al., Blood 2006;108:419.). Please see Appendix B for a table defining the response criteria for this study. Response criteria are determined by a morphologic count of the myeloblast population on aspirate smear. If an aspirate cannot be obtained, myeloblast percentage should be determined by morphologic and/or immunohistochemical staining of the bone marrow biopsy or alternatively determined by flow cytometry of a decalcified bone marrow biopsy sample.

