APPENDIX C**Response Criteria**

Category	Response criteria (responses must last at least 4 wk)
Complete remission (CR)	Bone marrow: \leq 5% myeloblasts with normal maturation of all cell lines
Partial remission (PR)	All CR criteria if abnormal before treatment except: - Bone marrow blasts decreased by \leq 50% over pretreatment but still $>$ 5% - Cellularity and morphology not relevant
Stable disease (SD)	Failure to achieve at least PR, but no evidence of progression
Disease Progression (DP)	For patients with: - Less than 5% blasts: \geq 50% increase in blasts to $>$ 5% blasts - 5%-10% blasts: \geq 50% increase to $>$ 10% blasts - 10%-20% blasts: \geq 50% increase to $>$ 20% blasts - 20%-30% blasts: \geq 50% increase to $>$ 30% blasts
Relapse after CR or PR	At least 1 of the following: - Return to pretreatment bone marrow blast percentage - Decrement of \geq 50% from maximum remission/response levels in granulocytes or platelets - Reduction in Hgb concentration by \geq 1.5 g/dL or transfusion dependence

From: Cheson, BD, et al. Blood. 2006;108:419-425.

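### The primary endpoint counts only death or relapse, and relapse requires a prior CR or PR, so a never-responder who progresses and is known to be alive at 18 months is scored failure-free

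*Combined protocol and SAP*

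**What the plan says.** Section 4.2.1 defines the primary endpoint as "18-month failure-free survival (failure defined as death or relapse", and section 11.1 repeats the same two events. Section 11.1 takes relapse from the International Working Group criteria. It refers the reader to Appendix B, but the table is in Appendix C.

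In Appendix C the relapse row is headed "Relapse after CR or PR". Progression has its own row, "Disease Progression (DP", based on rising marrow blasts. Stable disease is a third category: "Failure to achieve at least PR, but no evidence of progression".

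All patients start with active disease. Section 5.1.1 reads "Patients must have measurable disease requiring cytoreduction, defined as a bone marrow myeloblast count", with blasts of at least 5% and below 20%.

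The protocol expects progression. Section 7.4 has a rule that begins "If patients demonstrate disease progression at any point after the first cycle" and ends study treatment. For Arm B patients with stable or progressive disease after re-induction it says "the patient should be offered alternative treatment or proceed directly to transplant if possible". Section 8 has progression tracked during the 18 months, and section 12 has it recorded as an item separate from relapse and death. The 18-month column of Appendix D lists only survival and relapse. No section makes progression a failure.

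Section 13 declares success if observed 18-month failure-free survival (FFS) on hypomethylating agents (HMA) is at least as high as on intensive chemotherapy (IC), with 30 patients per arm.

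**The concern.** Two patients alive at 18 months with equally advanced disease can be scored in opposite ways. One reached a partial remission and lost it, and counts as a failure. The other never responded and progressed, and counts as a success. What separates them is response, which is measured after randomization and is affected by the treatments being compared. If the arms differ in the share of living never-responders who progressed, the endpoint credits the arm that has more of them.

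This matters for the main result because success is a bare comparison of two observed rates with 30 patients each. A difference of one or two patients between arms can decide it.

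**Working it through.** **1. Which patients are affected.** Reading sections 4.2.1 and 11.1 with Appendix C:

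| Course by 18 months | Scored |
|---|---|
| Died, with or without progression | Failure |
| Responded, then relapsed, alive (even if later in remission) | Failure |
| Never reached CR or PR, progressed, alive | Failure-free |
| Progressed, reached CR or PR on later therapy or transplant, then relapsed | Failure |
| Stable disease, alive | Failure-free |

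The third row is the gap. Stable-disease survivors are failure-free with or without the fix.

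**2. The plan's own figures.** Inputs from section 13: 30 per arm, success if the HMA count X(HMA) is at least the IC count X(IC), ties included. With independent binomials,

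P(success) = Σ over i ≥ j of Bin(i; 30, p_HMA) × Bin(j; 30, p_IC).

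- 50% vs 30%: 0.959 (stated 0.96)
- 45% vs 30%: 0.911 (stated 0.91)
- 50% vs 60%: 0.257 (stated 0.26)

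All three reproduce.

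**3. How far the definition could move the result.** The documents give no relevant rates, so everything in this step is assumed. Let the pool be the share of an arm alive at 18 months with progressed or relapsed disease, equal in both arms. Let r be the share of that pool who had responded first. Then

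scored FFS = disease-free share + pool × (1 − r).

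*Arms truly equal, 35% alive and disease-free in each.* With progression counted, P(success) = 0.55. For a 10% pool with r = 60% in IC and 30% in HMA, HMA scores 0.35 + 0.10 × 0.70 = 0.42 and IC scores 0.35 + 0.10 × 0.40 = 0.39.

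| Pool | r 60% IC, 30% HMA | r 30% IC, 60% HMA | r 60% in both |
|---|---|---|---|
| 5% | 0.60 | 0.51 | 0.55 |
| 10% | 0.64 | 0.46 | 0.55 |
| 20% | 0.73 | 0.37 | 0.55 |

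*HMA truly 10 points worse, 30% vs 40% disease-free.* With progression counted, P(success) = 0.25.

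| Pool | r 60% IC, 30% HMA | r 30% IC, 60% HMA | r 60% in both |
|---|---|---|---|
| 5% | 0.29 | 0.21 | 0.25 |
| 10% | 0.34 | 0.18 | 0.25 |
| 20% | 0.43 | 0.13 | 0.26 |

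In patients, the 10% pool in the first column credits 30 × 0.10 × 0.70 = 2.1 on HMA and 30 × 0.10 × 0.40 = 1.2 on IC, a net 0.9.

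**4. Section 13 if progression became a failure.** Take the stated rates as death-or-relapse rates and subtract an assumed share of living never-responder progressors from each arm.

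| Subtracted (HMA / IC) | 50/30 | 45/30 | 50/60 |
|---|---|---|---|
| none | 0.96 | 0.91 | 0.26 |
| 2% / 1% | 0.95 | 0.90 | 0.23 |
| 7% / 4% | 0.94 | 0.87 | 0.19 |
| 4% / 7% | 0.98 | 0.95 | 0.34 |
| 5% / 5% | 0.96 | 0.92 | 0.26 |
| 10% / 10% | 0.97 | 0.93 | 0.26 |

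At the extremes of 0 to 15% in each arm, the ranges are 0.71 to 0.999, 0.56 to 0.997, and 0.03 to 0.70.

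**The case against.** The best defence is that the trial compares initial strategies. Section 2.3 speaks of a treatment strategy, section 3.1 of initial therapy, and section 7.4 sends inadequate responders on to other treatment or transplant. On that view progression on the first regimen is a step on the path, and scoring a later rescued patient as a failure changes the question. The defence does not explain the asymmetry, because a responder who relapses and is then rescued by transplant still fails under the current text. It does justify keeping the death-or-relapse version as a sensitivity analysis.

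Three further objections stand in part.

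- **Size.** The affected group may be small. Progressors who die already count, and later remission opens the way to a countable relapse. At 2% and 1% the section 13 figures barely change. The sensitivity to a single patient comes from the point-estimate success rule, not from this definition.
- **Ascertainment.** Section 11.2 sets Arm B marrow at about day 28 or count recovery. In Arm A it only recommends marrow, after 2 to 4 cycles of decitabine or 4 to 6 of azacitidine, and marrow for suspected progression is optional. Making progression an event leans harder on this unequal schedule.
- **Missing status.** Section 7.4 withdraws patients who are no longer transplant candidates, and section 7.7 then seeks permission for survival data only. Some progressors will have incomplete records, so the finding is limited to those known to be alive.

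A reader might infer that the definition favours HMA, on the view that the less intensive arm has more non-responders. The documents give no response rates by arm, and the reversed split moves the result the other way. A reader might also infer that the section 13 probabilities are wrong, or that their endpoint is unspecified. Section 13 uses the defined term failure-free survival, so its rates read as death-or-relapse rates. Only the phrase about survival probabilities in the first scenario is loose.

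**Conclusion.** The gap holds on the text, with high confidence. A never-responder who progresses and is known to be alive at 18 months counts as a success, and a relapsed responder does not. The primary comparison is therefore exposed to a post-randomization difference in response.

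The consequence is not established. Under the assumptions shown, with truly equal arms, P(success) moves from 0.55 to between 0.51 and 0.60 for a 5% pool and to between 0.37 and 0.73 for a 20% pool. It is essentially unchanged when such patients are equally frequent in both arms. The pools and response shares are assumptions, and neither size nor direction can be read from the protocol. The stated 0.96, 0.91 and 0.26 are correct for the current endpoint. This should be fixed, but it does not show that the trial's result would be wrong.

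**What to change.** - **Sections 4.2.1 and 11.1:** define failure as the first of death from any cause, Appendix C disease progression, or relapse after CR or PR, in all randomized patients. Report the present death-or-relapse version as a sensitivity analysis, and 18-month overall survival of all randomized patients by arm beside it (section 4.2.2 lists overall survival only after transplant). Correct the section 11.1 cross-reference to Appendix C.
- **Section 13:** state that the assumed rates refer to the revised endpoint. If they were death-or-relapse rates, show the success probabilities over a stated range of living-progressor rates, as in step 4 of the working. A single restated figure would need inputs that the protocol lacks.
- **Data:** add progression to the 18-month column of Appendix D, and dates of progression, relapse and death to the Appendix H sheet, which has no such columns. Section 12 still points to Appendix I for this recording, and that appendix was deleted in the 28 May 2019 revision.
- **Section 7.7:** extend the post-withdrawal permission from survival to progression and relapse, with matching consent wording.

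The text and data changes are cheap, since sections 8 and 12 already call for progression to be tracked and recorded. Changing the primary endpoint of an open-label trial is still a substantive amendment, so it should be made before outcomes by arm are examined.

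Three downsides should be stated in the protocol. FFS will be somewhat lower. A patient who progresses and is later in remission will count as a failure. Ascertainment of progression will still differ between arms because marrow timing differs.
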